5 TRIAL SETTING

Historic data and stored samples from patients that consented to participate in the multicentre TARGET trial will be retrieved from NHS pathology laboratories and analysed at NBT.

6 PARTICIPANT ELIGIBILITY CRITERIA

IRAS ID 329574

All patients recruited for the TARGET study will be included, provided they have sufficient stored biopsy material to undertake the required additional tests.

TARGET eligibility required all of the following to apply:

- Pleural thickening on CT suspicious for pleural malignancy
- Have had any form of pleural biopsy in the last 12 months (either by thoracoscopy or under radiological guidance) which was non-diagnostic for cancer
- Lung Cancer/mesothelioma MDT decision to perform further CT-guided biopsy to pursue a diagnosis

Participants were ineligible for TARGET if ANY of the following applied:

- Unsuitable for a CT guided biopsy (inability to co-operate, lie still for the duration of the biopsy, uncorrectable coagulopathy, inability to tolerate a pneumothorax, severe underlying lung disease [patients with an FEV1 < 35% assessed using simple spirometry])
- Unable to give written informed consent
- Pregnancy or lactation
- Age<18 years
 Pleural thickening not amenable to a radiologically guided biopsy
- Talc pleurodesis in the previous 6 months

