13 ETHICAL AND REGULATORY CONSIDERATIONS	
14. DISSEMINATION POLICY	
15. REFERENCES	
16. APPENDICIES	

ii. LIST OF ABBREVIATIONS

BAP1 BRCA-associated protein 1

CA Competent Authority

CAG Confidentiality Advisory Group

CI Chief Investigator
CRF Case Report Form

FEV1 Forced expiratory volume in 1 second

FISH fluorescence in situ hybridisation

GCP Good Clinical Practice

GMP Good Manufacturing Practice

ICF Informed Consent Form

ICH International Conference on Harmonisation of technical

requirements for registration of pharmaceuticals for human

use.

IHC Immunohistochemical

ISF Investigator Site File (This forms part of the TMF)

ISRCTN International Standard Randomised Controlled Trials

Number

MDT Multi-Disciplinary Team

MTAP methylthioadenosine phosphorylase

NHS R&D National Health Service Research & Development

PI Principal Investigator

PIC Participant Identification Centre
PIS Participant Information Sheet

PET-CT Positron Emission Tomography CT

PPI Patient and Public Involvement

PM Pleural Mesothelioma
QA Quality Assurance
QC Quality Control

REC Research Ethics Committee
SDV Source Data Verification

SOP Standard Operating Procedure

SSI Site Specific Information

TMF Trial Master File

TMG Trial Management Group
TSC Trial Steering Committee

iii. TRIAL SUMMARY

Trial Title	Reducing Repeat Pleural Biopsies In Suspected Cancer – a study of the TARGET trial cohort			
Internal ref. no. (or short title)	REPLICA			
Trial Design	additional diagnostic tests in no could increase the diagnosis ramalignancy. Standard pathway	A UK based multicentre study to evaluate whether performing additional diagnostic tests in non-diagnostic pleural biopsies could increase the diagnosis rate in suspected pleural malignancy. Standard pathway vs proposed (involving additional diagnostic tests) pathway		
Trial Participants	A study of the 59 participants who enrolled in the RCT TARGET study at 8 UK sites between September 2015 and September 2018. Inclusion criteria included suspicious pleural thickening on CT scan, non-diagnostic pleural biopsy and MDT decision to perform further CT-guided biopsy to pursue a diagnosis.			
Planned Sample Size	59 participants were enrolled in TARGET. Total sample size is 118, as each participant provides matched data for both standard and proposed pathways. 129 biopsy samples available in total.			
Follow up duration	12 months (already completed as part of TARGET trial)			
Planned Trial Period	12-18 months total			

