We previously conducted a study of people with suspected PM who required further biopsies as their first biopsy did not diagnose the condition. All patients consented to be in this trial and an application is underway for approval to perform additional tests on the trial samples. We want to re-test their original and follow-up biopsy samples for BAP1, p16 and MTAP to see whether this would have made the diagnosis sooner and removed the need for further biopsies. We will investigate how many biopsies could have been avoided, how much time would have been saved, and what cost-savings this would have offered the NHS.

BAP1, p16 and MTAP are not routinely used in clinical practice and are not available at many hospitals, despite being relatively inexpensive. BAP1 is already available in NBT and MTAP is undergoing set up. The cost of setting up MTAP is between £150-£400.

We hope our research will show how useful these tests are and how much benefit they offer to patients and NHS services, so they can be used more widely in routine care. Ultimately, we expect our research to be included in national guidelines and change clinical practice across the UK and worldwide.

Scientific summary:

Pleural Mesothelioma (PM) is a primary incurable malignancy of the pleural surface, associated with prior asbestos exposure. Median survival is 9-12 months. Chemotherapy offers marginal therapeutic benefit, but combination immunotherapy has shown promise in recent phase III trials. [1, 2]

Diagnosing PM can be challenging. Radiology supports diagnosis but pathological diagnosis is the gold standard. Some patients present with pleural effusions but pleural fluid sensitivity for PM is low. Pleural biopsy has higher diagnostic sensitivity, but this drops with smaller samples and certain histological subtypes [3]. As a result, some patients undergo multiple investigations, with increased risk of complications and delays to treatment initiation.

Our research unit has previously studied potential approaches to enhance the PM diagnostic process. The multi-centre randomised TARGET trial studied whether Positron Emission Tomography CT (PET-CT) directed biopsy improved the diagnostic yield of biopsies in people with previous non-diagnostic biopsies [4]. PET-CT did not improve diagnostic rates and some repeat biopsies were also non-diagnostic, necessitating further invasive procedures.

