2.1 Assessment and management of risk

- Patients: no patients are being recruited as part of this study (we are using historic data and stored samples from a previous study where patients consented to their anonymous information being used for future research).
- Data: risk of missing data: there is a risk that some biopsy samples will be insufficient in size to undergo the stains required. In another study that required pulling of much older biopsies, less than 10% of samples were missing.

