10 STATISTICS AND DATA ANALYSIS

The independent variable is the availability of BAP1, p16 FISH and MTAP testing (binary; available *vs* not available). The primary outcome is identification of malignancy on biopsy (binary; diagnostic *vs* non-diagnostic), with diagnosis defined as i) histopathological confirmation on standard testing or ii) histopathological features of PM with demonstrated BAP1, p16 or MTAP deletion or iii) Multi-disciplinary Team (MDT) diagnosis. It is assumed that confirmation of a malignant diagnosis stops the diagnostic pathway with no additional biopsies required. Any subsequent biopsies for these participants will not be included in the analysis, preventing double-counting. Secondary outcomes include total number of biopsies required, time to diagnosis, stage at diagnosis, number of MDT discussions, biopsy-associated costs, biopsy-related adverse events and survival. Potential confounding variables include age, sex, biopsy method and tumour histology and these will be adjusted for, when possible, in the analysis.

Outcome measures will be tabulated for standard and proposed pathways and compared using descriptive statistics (including the McNemar test). Univariable and multivariable logistic regression will look for an association between the availability of these tests and likelihood of a diagnostic biopsy. The relationship between secondary outcomes and availability of the tests will be evaluated using adjusted and unadjusted regression analyses and time to event analysis (cox proportional hazard model).

Sample Size:

Total number of patients: 59

Total histological samples for analysis: 129 (all participants had multiple biopsies)

REPLICA

IRAS ID 329574

Each participant will be assessed as a case (proposed pathway) and as an internal control (standard pathway) generating two groups of 59 = 118 records for inclusion in the study

Sample size is determined by the number recruited to the TARGET study which demonstrated diagnostic sensitivity (without these additional tests) of 30%. A sample size of 118 (59 in each arm) will allow detection of an increased diagnostic rate of 60% with 95% confidence intervals of +/- 8.8% (based on BAP1 loss prevalence of 60%).

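### Making eligibility depend on sufficient stored tissue gives a tested-only yield, probably somewhat too high, while the sample size counts all 59 participants with no allowance for loss

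*Protocol*

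**What the plan says.** Section 6 of the protocol makes inclusion conditional: TARGET patients enter "provided they have sufficient stored biopsy material to undertake the required additional tests". It does not say whether the condition refers to the baseline biopsy or to any of a patient's biopsies.

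Section 2.1 treats shortage of tissue as a missing-data risk: "there is a risk that some biopsy samples will be insufficient in size to undergo the stains required". The only rate it gives comes from another study, on considerably older samples, where "less than 10% of samples were missing".

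The counts carry no such condition. The Trial Summary describes "A study of the 59 participants who enrolled in the RCT TARGET study", and Section 10 has each participant serve as case and internal control, "generating two groups of 59 = 118 records for inclusion in the study".

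Two other places bear on the point. The scientific summary in Section 1 states: "Pleural biopsy has higher diagnostic sensitivity, but this drops with smaller samples and certain histological subtypes". Section 3 has BAP1 and MTAP run on every biopsy, with p16 FISH added only when those two do not give a diagnosis.

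The protocol does not say how a participant with an untestable sample is scored on the primary outcome.

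**The concern.** The primary objective is to find patients in whom extra testing of the baseline biopsy would have made further invasive tests unnecessary. The relevant population is everyone with a non-diagnostic first biopsy. If that biopsy was too small to stain, the proposed pathway would have left the patient needing a repeat. That is a result of the pathway and belongs in the denominator. An eligibility rule that removes the patient answers a different question: the yield among samples that could be tested.

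The sequential testing rule could add to this. A small sample that is positive on BAP1 or MTAP needs nothing more and stays in. A negative one with no tissue left for FISH could be ruled insufficient and drop out. Whether tissue suffices could then depend on the result.

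The yield, the biopsies avoided and the costs saved all use this denominator, and Section 2 intends the results to inform national guidelines. Deferral to an analysis plan does not fully settle the matter: such a plan can define how missing results are handled, but it should not bring back people whom the protocol makes ineligible.

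**Working it through.** **Inputs.** From the protocol: 59 participants and 118 records (Trial Summary, Section 10); assumed proposed-pathway rates of 60%, 70% and 80% with 95% half-widths of 8.8%, 8.2% and 7.2% (Section 10); a standard-pathway rate of 30% (Section 10); under 10% of samples missing in another study (Section 2.1). Assumed here: the number excluded, x, and the yield q that the excluded would have had. The protocol gives neither.

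**1. The plan's own precision.** Half-width = 1.96 × √(p(1−p)/n), with n = 118:
- p = 0.60: 8.84% (stated 8.8%)
- p = 0.70: 8.27% (stated 8.2%)
- p = 0.80: 7.22% (stated 7.2%)

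The figures reproduce at 118 records, that is, with nobody excluded. With 6 excluded there are 2 × 53 = 106 records, and the same formula gives 9.33% at p = 0.60. Whether 118 paired records is the right n for precision is a separate question.

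**2. Size of the overstatement.** If the reported yield among 59 − x tested participants is p, the yield over all 59 is (p(59 − x) + qx)/59. The overstatement is therefore (p − q)x/59.

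The largest whole number below 10% of 59 is 5 (5/59 = 8.5%; 6/59 = 10.2%). With p = 60% and x = 5:

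| Yield q in the excluded | All-59 yield | Overstatement |
|---|---|---|
| 0% | 54.9% | 5.1 points |
| 30% | 57.5% | 2.5 points |
| 60% | 60.0% | 0 |

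With p = 60% and q = 0, over a range of x: x = 1 gives 59.0%, x = 3 gives 56.9%, x = 6 gives 53.9%, x = 9 gives 50.8%. The last two exceed the 10% figure in Section 2.1.

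Seen from the other side: if 35 of 59 (59.3%) were truly diagnostic and 5 non-diagnostic participants were dropped, the report would read 35/54 = 64.8%.

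**3. Paired comparison.** Exclusion removes both of a participant's records. As an illustration, take 18/59 on the standard and 35/59 on the proposed pathway, with all 17 discordant pairs favouring the proposed pathway. The difference is 17/59 = 28.8 points. Dropping 5 pairs that are non-diagnostic on both pathways gives 17/54 = 31.5 points. The exact McNemar p-value is 2 × 0.5¹⁷ ≈ 0.000015 in both cases, because concordant pairs do not enter it.

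**The case against.** Several counter-arguments have force.

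*Insufficient now is not insufficient then.* The study uses residual material from patients enrolled in 2015–2018. A block may be inadequate today because earlier testing used it up, although BAP1 and MTAP could have been run at the time. A reader might infer that every untestable sample is a failure of the proposed pathway. The documents do not support that, and scoring all of them as non-diagnostic could bias the yield downward. This stands and shapes the fix.

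*The direction is inferred.* Section 1 links sample size to the sensitivity of pleural biopsy in general. It says nothing about BAP1, MTAP or p16 results on archived tissue. A reader might take upward bias as established; it is plausible but conditional. The primary outcome also accepts standard histology and MDT diagnosis, so an untestable participant is not automatically non-diagnostic. Dropping someone who was diagnostic would lower the yield.

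*The loss rate is borrowed.* The under-10% figure concerns missing samples in another study. It covers neither undersized samples nor participants. Overstatements of 6 to 9 points at a 60% yield require 6 to 9 exclusions, above that figure, with every excluded patient non-diagnostic.

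*The clause is ambiguous.* There are 129 samples, and every participant had more than one biopsy. If any adequate biopsy qualifies, a patient with a small baseline sample stays in. This stands, and it is itself a reason to reword the clause.

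*59 is a ceiling.* Section 10 takes the number from TARGET recruitment, so a reader who calls it a flat contradiction goes too far. The two statements agree if every patient has enough tissue. What remains is that no allowance for loss is made, although Section 2.1 expects some.

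**Conclusion.** The point holds in a limited form. As written, the plan conditions entry on tissue, expects some tissue to be too small, and still counts all 59 participants. Followed literally, it gives a tested-only yield for a question about all patients with a non-diagnostic first biopsy. That yield, and the biopsies and costs avoided, are probably overstated, provided that the clause is applied to the baseline biopsy and that those excluded are lower-yield than the rest.

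The size cannot be determined from the protocol. At a reported 60% with at most 5 of 59 excluded, it lies between zero (excluded patients have the same yield as the rest) and about 5 points (all non-diagnostic). The McNemar test is unaffected where the dropped pairs are non-diagnostic on both pathways, so the concern is with the estimates more than with that test. The loss of precision is small: about ±9.3% instead of ±8.8% at 106 records by the protocol's own method.

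**What to change.** In Sections 6 and 10:

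1. Include all 59 TARGET participants. State that the tissue condition governs whether the baseline biopsy can be tested, and does not govern eligibility.
2. In the all-59 analysis, count a baseline biopsy that was inherently too small as having no additional-test diagnosis, with the standard histology and MDT criteria still applying. State that a sample negative on BAP1 and MTAP with no tissue left for FISH stays in the analysis.
3. Handle blocks that are lost, or exhausted by earlier use, separately, with best-case and worst-case bounds.
4. Report the tested-only yield as a secondary result, with the numbers of untested samples and the reasons.
5. Say that the 59/118 precision figures assume no loss, and give the half-width at a plausible lower count, for example about ±9.3% at 106 records by the same method.

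This takes a few sentences and no new samples, though the reason for each untestable block has to be recorded. It is best settled before staining results are known. The price is a slightly lower or wider reported yield.

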7 TRIAL PROCEDURES

7.1 Recruitment

Patients will be identified from the TARGET trial database.

7.2 Consent

All patients in the study consented take part in the TARGET trial. They consented to have their anonymised data used in future research. Patients will have died by the time of this study, therefore we will not be able to obtain additional consent for use of non-anonymised data or biopsy samples. This study therefore requires CAG and ethical approval to access identifiable patient information while processing patient samples, so findings can be linked with clinical outcomes. TARGET consent form enclosed (Appendix 1)

7.3 Data extraction

Baseline clinical information and follow up data from visits at 3, 6 and 12 months will be extracted from the trial database. Where this data is unavailable, it will be sought from medical records. Variables include:

- Baseline demographic data
- Asbestos exposure history
- Relevant medical background
- Biopsy dates and results
- Biopsy method
- Number of biopsies required for diagnosis
- Biopsy-related adverse events
- Histological diagnosis
- Whether diagnosis was tissue based or clinico-pathological.
- Time to diagnosis (from enrolment)
- Stage at diagnosis
- Number of MDT discussions

- MDT outcomes including ultimate MDT diagnosis and date of diagnosis
- Radiological images and reports used during diagnostic period
- Anti-cancer treatment received
- Healthcare utilisation
- Overall survival

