	Objectives	Outcome Measures		
Primary	Identify patients for whom additional pathological testing would have yielded a definitive diagnosis on baseline biopsy, avoiding the need for further invasive tests	Identification of malignancy on biopsy (binary; diagnostic vs non-diagnostic) via: i) histopathological confirmation on standard testing or histopathological features of PM with demonstrated BAP1, p16 or MTAP deletion or iii) Multi-disciplinary Team (MDT) diagnosis		
Secondary	i) Investigate whether additional pathological testing would have shortened the overall time to diagnosis and ii) Investigate whether additional testing would have reduced costs	i) Total number of biopsies required ii) Time to diagnosis iii) Stage at diagnosis iv) Number of MDT discussions required v) Biopsy-associated costs vi) Biopsy-related adverse events		

in whom additional testing would have provided a definitive diagnosis

iv. FUNDING AND SUPPORT IN KIND

FUNDER(S) (Names and contact details of ALL organisations providing funding and/or support in kind for this trial)	FINANCIAL AND NON FINANCIALSUPPORT GIVEN
Southmead Hospital Charity [name] [contact]	Research grant
NBT NHS Trust	Salaries for [name], [name], [name], [name]
NIHR	Salary for [name]
University of Bristol	Salary for [name]
University of West of England	Salary for [name]

v. ROLE OF TRIAL SPONSOR AND FUNDER

The Sponsor and Funders have no role or remit in the study design, conduct, data analysis and interpretation, manuscript writing or dissemination of results.

vi. ROLES AND RESPONSIBILITIES OF TRIAL MANAGEMENT COMMITEES/GROUPS & INDIVIDUALS

Study management group:

Responsible for oversight of the study. It will monitor trial progress, ensure all practical details of the trial are progressing well and feed back to the sponsor. The study management group will be chaired by the CI and will include all members of the named research team. It will meet 4 times during the study period.

Patient and Public Involvement group:

IRAS ID 329574

This will involve a specialist nurse and trial co-ordinator communicating details of the trial progress to a group of mesothelioma patients and carers as the study progresses.

Study delivery group:

This involves the people responsible for retrieving histological samples and performing and reporting the pathological tests. They will ensure accuracy and reproducibility of the tests, and updating the investigators on progress.

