2 RATIONALE

This study aims to evaluate the diagnostic benefit of BAP1, p16 FISH and MTAP in suspected PM by re-testing the initial non-diagnostic/negative biopsy samples from TARGET trial participants to evaluate whether the additional tests would have yielded a definitive diagnosis sooner. If we demonstrate that running these inexpensive tests leads to earlier diagnoses and reduces the need for repeat biopsies, wider adoption of this test panel into routine clinical practice will follow. Our research will inform subsequent national guidelines, leading to changes in mesothelioma MDTs across the country. This will benefit patients (through shortened diagnostic pathways) and the NHS (through cost-savings and increased availability of biopsy appointments).

PPI representatives were universally supportive of the study, citing the potential benefits to them of fewer biopsies, reduced waiting time for a diagnosis, reducing stress and worry from non-diagnostic biopsies and reduced anxiety from all these factors.

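### Time to diagnosis is counted from TARGET enrolment, so a diagnosis made by re-testing the initial biopsy would normally fall before time zero and cannot properly enter the planned Cox model

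*Protocol*

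**What the plan says.** - **Origin.** The variable list in Protocol Section 7.3 gives "Time to diagnosis (from enrolment)". The trial summary, Section 3 and Section 10 also name time to diagnosis, but none gives an origin.
- **What came before enrolment.** Section 6 lists two conditions of TARGET entry: "Have had any form of pleural biopsy in the last 12 months (either by thoracoscopy or under radiological guidance) which was non-diagnostic for cancer" and "Lung Cancer/mesothelioma MDT decision to perform further CT-guided biopsy to pursue a diagnosis".
- **Which biopsy is re-tested.** The primary objective in the trial summary is to find participants in whom "additional pathological testing would have yielded a definitive diagnosis on baseline biopsy, avoiding the need for further invasive tests". Section 2 describes "re-testing the initial non-diagnostic/negative biopsy samples from TARGET trial participants". Section 3 applies the BAP1 and MTAP stains to repeat biopsies as well.
- **When the pathway ends.** Section 10: "It is assumed that confirmation of a malignant diagnosis stops the diagnostic pathway with no additional biopsies required".
- **Analysis.** For secondary outcomes Section 10 plans adjusted and unadjusted regression and "time to event analysis (cox proportional hazard model)".
- **Dates available.** Section 7.3 also extracts the dates of the biopsies and of the MDT diagnosis.

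**The concern.** The study asks whether extra stains on the first biopsy would have brought the diagnosis forward. The clock starts only after that biopsy has been taken, reported as non-diagnostic and discussed at an MDT. A participant who gains most, because the first biopsy becomes diagnostic, therefore has an event before the clock starts. A Cox model has no proper place for an event before its origin, since nobody is yet at risk. In practice the analyst would have to drop or truncate these records, a choice the protocol does not make and which could then be made with results in view.

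At stake is the first secondary objective, whether the diagnostic pathway would have been shorter. Section 1 promises to report the time saved, and Section 13.3 records that patient representatives stressed this outcome.

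**Working it through.** The protocol gives no figure for time to diagnosis, so there is none to reproduce. The check is date arithmetic for one participant re-diagnosed on the initial biopsy.

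**Notation**
- g = days from initial biopsy to enrolment. Section 6 gives only a ceiling of 12 months, about 365 days.
- r = days from that biopsy to the proposed-pathway report. Not in the protocol; 10 days is assumed below.
- t = days from enrolment to standard-pathway diagnosis. Not in the protocol; varied below.

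**Origin at enrolment**
- Proposed-pathway time = r − g. Standard-pathway time = t.
- The proposed time is negative whenever r < g. Entry required a known non-diagnostic result and an MDT decision, so this is the normal case. It would fail only if the extra tests took longer to report than the whole interval g.
- True saving = t − (r − g) = t + g − r.
- If negative times are set to zero, the recorded saving is t. The loss is g − r days, a share (g − r)/(t + g − r). This exceeds one half only when g − r > t.

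**Share lost by setting to zero (r = 10 assumed)**

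| g | t | true saving | recorded | share lost |
|---|---|---|---|---|
| 14 | 365 | 369 | 365 | 4/369 = 1% |
| 14 | 90 | 94 | 90 | 4/94 = 4% |
| 30 | 30 | 50 | 30 | 20/50 = 40% |
| 60 | 90 | 140 | 90 | 50/140 = 36% |
| 90 | 90 | 170 | 90 | 80/170 = 47% |
| 180 | 90 | 260 | 90 | 170/260 = 65% |
| 365 | 90 | 445 | 90 | 355/445 = 80% |
| 365 | 14 | 369 | 14 | 355/369 = 96% |

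**Effect on a Cox fit (one simulated data set, all inputs assumed).** 59 pairs; g uniform on 14 to 365 days; t = 7 days plus an exponential with mean 60; each participant re-diagnosed on the initial biopsy with probability 60%; r = 10; no censoring. This gave 37 re-diagnosed participants. All 37 had negative times, as they must when the smallest g (14) exceeds r (10).

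| Handling | records | hazard ratio | mean saving, days |
|---|---|---|---|
| Origin at initial biopsy | 118 | 2.28 | 161 |
| Enrolment, negatives set to 0.5 day | 118 | 2.37 | 43 |
| Enrolment, negatives dropped | 118 − 37 = 81 | 1.28 | 0 in the remaining pairs |

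Truncation hardly moved the hazard ratio here, because the Cox model uses only the order of the times, but it removed (161.0 − 42.6)/161.0 = 74% of the days saved. Dropping the records damaged both measures. If the signed times are kept, the paired difference is still 161 days, because the origin cancels.

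**Origin at initial biopsy.** Proposed time = r, standard time = g + t, saving = g + t − r. All times are positive and none of the saving is cut off.

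**The case against.** The strongest reply is that Section 7.3 is an extraction list. The item may mean only the interval recorded under the standard pathway; the proposed-pathway time is counterfactual and has to be derived, and that derivation may belong to an analysis plan not seen here. The dates needed are already being collected. The protocol nowhere proposes dropping or truncating records, and it also plans descriptive comparisons and regressions that need not fail.

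Part of this stands. The problem lies in the time-to-event analysis and in any dropping or truncation. A signed paired difference escapes it. So do participants newly diagnosed only on a repeat biopsy after enrolment, who keep valid positive times. The primary outcome is binary and does not use this variable.

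The rest does not remove the point. Enrolment is the only origin stated, and it conflicts with the protocol's own entry criteria, objective and model. An analysis plan that follows it inherits the problem; one that corrects it departs from the protocol.

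Two stronger readings are tempting. A reader might infer that most of the time saved is lost. The documents do not support this: they give neither g nor t, 12 months is only a ceiling on g, and the share lost by truncation runs from about 1% to 96% over the assumed values. A reader might also infer that the outcome cannot be computed for anyone who benefits. The post-enrolment diagnoses and the signed difference show otherwise.

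**Conclusion.** The point holds for participants whose initial biopsy becomes diagnostic with the additional tests. With enrolment as origin, their proposed-pathway diagnosis would normally precede time zero, and these records cannot properly enter the planned Cox model. Dropping them removes participants who benefit. Setting them to zero loses g − r days each, at most about 12 months. The actual loss cannot be sized from the protocol, and the percentages and hazard ratios above only illustrate the mechanism. The conclusion about order rests on the entry criteria and on the extra tests being reported in less time than the biopsy-to-enrolment interval. One secondary outcome is affected. It should be settled before the analysis begins.

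**What to change.** In Sections 7.3 and 10:

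1. Set time zero for both pathways at the date of the initial non-diagnostic pleural biopsy, and say which biopsy is meant if more than one preceded enrolment.
2. Define the proposed-pathway diagnosis date as the date of the biopsy that becomes diagnostic plus a stated reporting turnaround. Vary the turnaround in a sensitivity analysis that covers participants who need p16 FISH after BAP1 and MTAP.
3. Report the within-participant difference in days alongside the Cox model.

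The cost is wording in two sections and one turnaround assumption, for which the protocol gives no figure. No new samples or variables are needed, because the biopsy and diagnosis dates are already on the extraction list.
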